11.6 Additional Safety and Effectiveness Endpoints

The endpoints in this section will be evaluated according to the general statistical methods described in section 11.8. These endpoints will not be subject to the formal multiple comparisons correction; they are presented as part of the totality of information. All the statistical tests between the treatment arms will be two-sided tests at $\alpha=0.05$.

- Mortality (all cause & cardiovascular) at 30 days and 1 year
- Stroke (disabling and nondisabling) at 30 days and 1 year
- Death or stroke at 1 year
- Death or disabling stroke at 30 days and 1 year
- Vascular complications (major) at 30 days and 1 year
- Bleeding complications (life threatening, disabling or major) at 30 days and 1 year
- Myocardial infarction at 30 days and 1 year
- Acute kidney injury at 30 days
- Requirement for renal replacement therapy at 1 year
- New permanent pacemaker implantation resulting from new or worsened conduction disturbances at 30 days and 1 year.
- Coronary obstruction requiring intervention at 30 days and 1 year

- New York Heart Association class at 30 days and 1 year
- Hemodynamic valve performance evaluation by echocardiography for aortic valve stenosis and aortic valve regurgitation at 30 days and years 1, 2, 3, 4, 5, 7, and 10. Echo readings to be evaluated include aortic valve area, mean gradient, peak gradient, perivalvular aortic regurgitation, total aortic regurgitation, and mitral regurgitation.
- Rehospitalization (valve-related or procedure-related and including heart failure) at 30 days, 1 year and annually (up to 10 years)
- Days alive and out of hospital at 1 year
- Six-minute walk test at 30 days and 1 year
- Health status as evaluated by Quality of Life questionnaires at 30 days and 1 year
- New onset atrial fibrillation at 1 year
- ICU days and discharge location
- Structural valve deterioration at years 1-5,7 and 10

11.7 Additional analyses

- Baseline data will be reported by summary statistics, separately by trial arm with p - values.
- The various procedural variables will be reported by summary statistics, separately by trial arm with p -values.
- Visit compliance data will be presented.
- Analysis of echo and procedural variables will be presented by valve size, at the various echo collection time points.
- Analyses past one year will be the same as the analyses for 1 year, but limited to those variables collected after the 1 year visit.

11.8 General Statistical Methodology

11.8.1 Time Dependent Variables

Time-dependent variables will be analyzed using the Kaplan-Meier algorithm, with standard errors computed by Greenwood's formula. The number of patients-at-risk will be computed at exact time points, without reference to any nominal follow-up windows. The log-rank statistic will be used for any comparison among groups.

Thirty day analysis will present both pure frequency and Kaplan-Meier rates; for later analyses only Kaplan-Meier rates will be presented. Kaplan-Meier rates will be presented at 30 days and 1 year as well as other time points as appropriate.

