11.8.7 Adverse event analysis

- Adverse event analysis will involve both site and CEC reporting.
 - Where events have been adjudicated by the CEC, those adjudications will be used in preference to site reports.
 - Where site events are analyzed, the MedDRA coding will be used. The underlying site evaluations will not be used for analysis, but may appear in listings as appropriate.
- Adverse events to be analyzed include the composites involved in the primary and secondary endpoints, as well as all events contained in these composites. All events adjudicated by the CEC will also be analyzed.
- Adverse event tables will present data at 30 days, 6 months, and 1 year. The tables will include counts of events, patients with event, and Kaplan-Meier event rates at the specific time point. The trial arms will be compared by the log-rank test
- Late adverse events (> 30 days) will be analyzed by a constant hazard model, and upper one-sided confidence limits will be given for the rates.

- Adverse event data past 1 year will be presented as counts of events and patients with event. No formal analyses will be performed for such data.

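### Past 1 year the protocol gives two conflicting rules for rehospitalisation, no method for structural valve deterioration, and no handling of death for either

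*Combined protocol and SAP*

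**What the plan says.** Section 11.6 lists rehospitalisation at 30 days, at 1 year and then every year to year 10, and "Structural valve deterioration at years 1-5,7 and 10". It sends these endpoints to the methods of section 11.8, with two-sided tests at 0.05 and no multiplicity adjustment.

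Section 11.7: "Analyses past one year will be the same as the analyses for 1 year", restricted to variables still collected after the 1-year visit.

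Section 11.8.1 prescribes Kaplan-Meier with Greenwood standard errors for time-dependent variables. It adds "The log-rank statistic will be used for any comparison among groups" and, for anything after 30 days, "for later analyses only Kaplan-Meier rates will be presented".

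Section 11.8.7 sets its scope as follows: "Adverse events to be analyzed include the composites involved in the primary and secondary endpoints, as well as all events contained in these composites". Up to 1 year it gives counts, Kaplan-Meier rates and a log-rank test. It then says "Late adverse events (> 30 days) will be analyzed by a constant hazard model", with no end date. Its last bullet reads: "Adverse event data past 1 year will be presented as counts of events and patients with event". On testing or modelling of this material, the same bullet is explicit: "No formal analyses will be performed for such data".

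The only statement on censoring is in section 11.8.4. It concerns the primary composite, in which death is itself an event.

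**The concern.** A statistician programming the year-2 report cannot tell whether rehospitalisation gets a Kaplan-Meier curve with a log-rank test or a bare count. For SVD the choice is wider still, because Kaplan-Meier, Fisher's exact test on a binary variable, or counts could each be defended after the data are seen.

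The silence on death matters because follow-up runs to 10 years. A patient who dies can no longer be rehospitalised or develop valve deterioration. A single-endpoint Kaplan-Meier analysis treats that death as censoring, so 1-KM estimates the risk in a setting where nobody dies. That is higher than the proportion of patients who actually have the event. Counts have a different weakness, since they ignore follow-up time. Durability and readmission are central long-term questions for a bioprosthesis in low-risk patients, so the absolute rates will be read closely.

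**Working it through.** **Text.** Rehospitalisation is a component of the primary composite, so 11.8.7 covers it.

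- *11.6, 11.7 and 11.8.1:* tested annually to year 10, by the same analysis as at 1 year, with Kaplan-Meier and log-rank. These three sections agree with one another.
- *11.8.7, last bullet:* past 1 year, counts only and nothing formal.

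That makes two rules in direct conflict. The constant-hazard model can sit alongside Kaplan-Meier; it conflicts with the last bullet only if it is run past 1 year, which is not stated.

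SVD is not called time-dependent, categorical or an adverse event anywhere in 11.8.

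**Size.** The plan gives no figure for analyses past 1 year, so there is none to reproduce. Its sample size of 864 (section 11.1) does reproduce, at 432 per arm with 90.0% power, and is not touched by this point.

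Inputs: the documents give no 10-year rates of death, SVD or rehospitalisation in low-risk patients. The assumed constant hazards are death 1-7% per year, SVD 0.5-3% per year and rehospitalisation 3-8% per year. Death at 1-7% per year means 10-year mortality of 1 − exp(−0.1) = 9.5% to 1 − exp(−0.7) = 50.3%.

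With event hazard h and death hazard d over t years:

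- 1-KM with deaths censored = 1 − exp(−ht)
- cumulative incidence = h/(h+d) × [1 − exp(−(h+d)t)]

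Example, h = 0.01, d = 0.05, t = 10: 1-KM = 1 − exp(−0.1) = 9.5%; cumulative incidence = (0.01/0.06) × [1 − exp(−0.6)] = 7.5%.

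Results at 10 years:

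| Event hazard per year | 1-KM | Cumulative incidence with death at 1 / 3 / 5 / 7% per year |
|---|---|---|
| SVD 0.5% | 4.9% | 4.6 / 4.2 / 3.8 / 3.5% |
| SVD 1% | 9.5% | 9.1 / 8.2 / 7.5 / 6.9% |
| SVD 2% | 18.1% | 17.3 / 15.7 / 14.4 / 13.2% |
| Rehospitalisation 5% | 39.3% | 37.6 / 34.4 / 31.6 / 29.1% |
| Rehospitalisation 8% | 55.1% | 52.7 / 48.5 / 44.8 / 41.4% |

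Over the whole grid the relative overstatement is about 0-4% at 1 year, 2-18% at 5 years and 4-39% at 10 years. In absolute terms it is at most 0.26 points at 1 year, and 0.2 to 13.6 points at 10 years.

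Checks:

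- Fixing 1-KM at 10% at 10 years, with 10-year mortality of 20, 30, 40 or 50%, gives cumulative incidence of 9.0, 8.4, 7.9 or 7.3%.
- A simulation of 200,000 patients (h = 0.02, d = 0.05) gave 1-KM of 18.2% against an actual 14.4%.
- With a late-rising SVD hazard and 1-KM of 10%, cumulative incidence is 9.4, 8.7, 7.4 or 6.6% at mortality of 10, 20, 40 or 50%.
- As an illustration only, the earlier high-risk/inoperable cohort (Table 1.2.1-5) had 14.4% mortality and 17.1% rehospitalisation at 1 year. Treating 17.1% as 1-KM with constant hazards gives an incidence of about 15.9%. That population is much sicker than this one.

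**The case against.** The counts-only bullet may be deliberate. Section 12.3 ends event adjudication at the primary endpoint, and section 9.5 narrows adverse event reporting after year 1. That could explain the bullet, but it does not remove the conflict, because 11.6 still schedules rehospitalisation annually to year 10 with tests.

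A reader might infer that the arm comparison is biased. The documents do not support this for the planned test: with deaths censored, log-rank is a valid test of cause-specific hazards. If SVD hazards are equal, 1-KM is equal in both arms whatever the mortality. In the example above, arms with the same 10% 1-KM but mortality of 20% and 40% would show cumulative incidence of 9.0% and 7.9%, so the arm with more deaths would look more durable. The two quantities answer different questions, and only the reading of 1-KM as the proportion of patients affected is wrong.

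A reader might also conclude that SVD will be overstated. That is not shown. SVD is listed at the echo years and could equally be analysed as a binary variable under 11.8.3. What stands is that its method is missing.

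Finally, 11.8.5 refers to a SAP, but the documents contain no separate SAP text beyond protocol section 11. Death handling could be defined there.

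**Conclusion.** The conflict for rehospitalisation past 1 year is established from the text, as is the missing method for SVD. It would overstate matters to call this three incompatible specifications, since 11.6, 11.7 and 11.8.1 agree and only the last bullet of 11.8.7 departs from them.

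Censoring of deaths is inferred from how plain Kaplan-Meier works; the protocol does not state it. If it is done, the direction is certain: any mortality above zero makes 1-KM exceed the proportion of patients with the event. The size is not certain. It is negligible at 1 year and lies between 4% and 39% relative at 10 years, all under assumed hazards.

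The primary composite includes death and is unaffected. These endpoints lie outside the labelling hierarchy, so no error-rate claim is at stake. The point should still be settled before the first report past 1 year.

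**What to change.** - **11.8.1:** report rehospitalisation and SVD at every scheduled time point, including year 1, as Aalen-Johansen cumulative incidence with death as a competing event, by arm with 95% confidence intervals. Using it at year 1 as well avoids a series that changes estimator at year 2. 1-KM may be shown as a supplement.
- **Test:** keep the planned log-rank test as the single comparison and describe it as cause-specific. Do not leave a choice between it and Gray's test, which addresses a different hypothesis.
- **Kaplan-Meier:** keep it for all-cause death and for composites that include death.
- **11.8.7, last bullet:** exempt only rehospitalisation and SVD, the two event endpoints that 6.3 and 11.6 schedule past 1 year. A wider exemption would open late formal analyses of events, such as myocardial infarction and bleeding, that are defined only at 30 days and 1 year.
- **11.8.7, constant-hazard model:** state whether it stops at 1 year.

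The cost is protocol and SAP wording and a small amount of extra analysis in standard software. No new data are needed and the sample size does not change. Reported rates will be somewhat lower than 1-KM.

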11.8.2 Continuous and ordinal variables

- For continuous variables, summary statistics will include means, standard deviations, medians and quartiles. Confidence limits will be computed using the t -distribution. Groups will be compared using t-tests or analysis of variance. Where severe departures from normality are observed, comparisons will also be performed using the Wilcoxon rank-sum test.
- For ordinal variables, summary statistics will include medians and quartiles; means will also be presented when appropriate. Group comparisons will be performed using the Wilcoxon rank-sum test.
- NYHA and regurgitation will be considered as ordinal variables. Group counts and means will be presented for these variables.

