4.0 ENROLLMENT

Up to 1182 qualified patients will be randomized at up to 65 actively enrolling sites in the US. It is anticipated that approximately 5-10 sites may be selected outside of the US. Further, up to ten (10) separate US sites from targeted geographic areas will be selected to enroll patients in a single-arm registry for underrepresented populations. No site will be allowed to enroll more than 15% of patients. Edwards will notify investigative sites of enrollment closure.

Sub-studies

Of the 1182 patients, a subset of patients will also be enrolled in the following randomized sub-studies:

- CT sub-study (up to 440)
- Actigraphy/QOL sub-study (up to 400) [Enrollment Closed]

Registries

Additional patients will be enrolled in the following single-arm registries:

- Alternative Access Registry (100) [Enrollment Closed]
- Bicuspid Registry (up to 75)
- Underrepresented Populations Registry (up to 100)

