- Left heart catheterization to assess the severity of aortic stenosis and severity of coronary artery disease, if applicable. Qualifying catheterization must be performed within 1 year prior to randomization, unless clinically indicated.
- SYNTAX Score for significant native coronary artery disease (CAD)
- Pulmonary Function Test for patients with a history of lung disease

Neurological Assessments:

- Mini Mental State Examination (MMSE), (Appendix G)
- National Institutes of Health Stroke Scale (NIHSS), (Appendix H)
- Modified Rankin Scale (mRS), (Appendix I)

Every effort should be made to have a neurologist (or neurology fellow) perform the NIHSS and mRS assessments. If it is not possible to have the neurologist/fellow perform the assessments within the protocol-specified visit window, a certified study team member may perform the assessments.

Functional Assessments:

- Six Minute Walk Test (6MWT), (Appendix E)
- Frailty Index (5 Meter Walk Test (5MWT), grip strength, Activities of Daily Living (ADL), and Albumin laboratory) (Appendix F)
- Quality of Life Assessments
 - KCCQ (Appendix N)
 - EQ-5D-5L (Appendix M)
 - SF-36 (Appendix O)

Clinical Laboratory Tests:

- WBC, Hgb, and platelet count
- PT or INR
- CK/CKMB and/or troponins \leq 72 hours before the valve implant procedure
- Creatinine
- eGFR
- Albumin (as part of Frailty Index)
- Total Bilirubin
- AST/ALT (required for patients with chronic liver disease)
- B-type natriuretic peptide (BNP)

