11.0 STATISTICAL ANALYSIS

11.1 Sample Size Calculations

The sample size for the trial is based on obtaining at least 90% power to pass the 1-year safety and effectiveness endpoint.

Event rate estimates for the primary safety and effectiveness endpoint were based on data from prior studies. Since the current study patients are a lower risk

population, and to account for procedural refinement over time in both arms as well as changes in definitions for components of the endpoint, the rates have been lowered.

The sample size is based on the composite primary endpoint which assumes an event rate of 16.6% in the SAVR arm and 14.6% in the TAVR arm. A randomized sample size of 864 patients with 1-year data would produce 90% power for passing the endpoint. The test statistic used for this computation is the one-sided Z test (Unpooled), at $\alpha = 0.025$, using the specified non-inferiority margin of 6.0%. The sample size was computed in PASS.

The sample size determination was based on a pure frequency analysis, whereas the endpoint analysis will use the Kaplan-Meier estimates. Since the two methods are equivalent in the absence of censoring, and a sufficient number of uncensored patients is anticipated, the sample size should be adequate.

Because the feasibility assumptions are uncertain in this previously unstudied population, an actual sample size of 1000 has been chosen, which is higher than the minimum statistically justified size to allow for trial contingencies, such as withdrawals and lost to follow-up.

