11.4 Primary endpoint analysis (Non-inferiority)

The primary safety and effectiveness endpoint is the composite of all-cause mortality, all stroke, and rehospitalization (valve-related or procedure-related and including heart failure) at 1 year post procedure. The endpoint will be evaluated as a non-inferiority analysis based on a non-inferiority margin of 6.0%. The components of

the composite endpoint will be evaluated by the CEC.

To precisely formulate the test, let r_T denote the true event proportion in the test arm at 1 year, and r_C denote the true event proportion in the Control arm at 1 year. The hypotheses are:

$$\begin{aligned} H_0: r_T - r_C &\geq \Delta \\ H_A: r_T - r_C &< \Delta \end{aligned}$$

The value Δ is the non-inferiority margin, and is taken to be 0.06. The test will be performed as a one-sided test at $\alpha = 0.025$.

A 95% confidence interval for the difference $r_T - r_C$ will be computed using the Kaplan-Meier algorithm with the standard errors being computed using Greenwood's formula. The null hypothesis shall be rejected at $\alpha = 0.025$ if the upper confidence limit is less than 0.06.

Covariates will not be included in analysis of the primary endpoint.

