11.8.9 Quality of life questionnaires

Quality of life questionnaires will be scored according to algorithms provided by the vendor. The various summary scores produced by the algorithms will be analyzed as continuous variables.

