12.4.3 Quality of Life Questionnaires

Investigational sites will be provided with paper QoL questionnaires (KCCQ, EQ-5D-5L, and the SF-36). Patient questionnaires will be IRB approved prior to patient administration.

Investigational staff will administer patient questionnaires to study patients. Patients will be instructed to complete each questionnaire at visits specified in section 8.0. The patient will be instructed by the investigational staff to sign and date the paper questionnaire once the questionnaire is completed. Patients will be instructed by the investigational staff not to change questionnaire answers once the questionnaire has been completed. Investigational sites should retain the completed questionnaire in the patients' source documents. Site staff will enter data collected from the completed patient questionnaire into the EDC.

The patient level summary scores will be computed by the Edwards Biostatistics group, and these scores will be used in evaluating protocol endpoints. A QoL core lab may prepare reports of additional analyses.

Quality of life will be measured through standard surveys:

- 1) The Kansas City Cardiomyopathy Questionnaire (KCCQ) is an assessment of disability and quality of life impairment due to congestive heart failure.
- 2) EQ-5D-5L is a standardized questionnaire for describing and valuing patients' health-related quality of life for clinical and economic appraisal.

- 3) The SF- 36 is a generic health status instrument and rating scale that allows mapping of health status to population-level utility weights. This is an important metric for cost- effectiveness analysis.

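### Continuous quality-of-life scores and six-minute walk distance are compared without baseline adjustment, although baseline is collected for all of them before randomisation

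*Combined protocol and SAP*

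**What the plan says.** Section 11.6 lists "Six-minute walk test at 30 days and 1 year" and the quality-of-life questionnaires at the same two visits. It refers them to section 11.8, with two-sided tests at 0.05 and no formal multiplicity correction. Section 11.8.9 says of the questionnaires: "The various summary scores produced by the algorithms will be analyzed as continuous variables". Section 12.4.3 adds that "these scores will be used in evaluating protocol endpoints". Section 11.8.2 then gives the test for continuous variables: "Groups will be compared using t-tests or analysis of variance". A Wilcoxon rank-sum test is added where departure from normality is severe.

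No ANCOVA, mixed model or baseline covariate is named for these measures. The only statement about covariates is in section 11.4: "Covariates will not be included in analysis of the primary endpoint". It does not reach the continuous endpoints.

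The screening list in section 8.1 and the Schedule of Procedures both require the six-minute walk, KCCQ, EQ-5D-5L and SF-36 at screening. Section 8.2 requires screening to be complete before a patient is randomised.

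**The concern.** With two arms, a one-way analysis of variance is the t-test, so that wording does not bring baseline in, and the Wilcoxon test does not use it either. A pre-randomisation value of the same measure usually predicts the follow-up value. Leaving it out makes the confidence intervals for the arm differences wider than the collected data allow. What is lost is precision, not validity.

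The text also leaves the analysed variable unclear. For the questionnaires, sections 11.8.9 and 12.4.3 point towards the visit score without saying so outright. For the six-minute walk, section 11.6 names only the visits, so visit value and change from baseline both remain possible. ANCOVA settles this, because adjusting for baseline gives the same arm difference whichever of the two is the outcome.

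Section 11.7 will report baseline data by arm with p-values, and section 12.4.3 lets a core lab prepare further quality-of-life reports. Without a pre-specified adjustment, a chance imbalance could prompt post hoc adjusted results that compete with the planned ones.

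**Working it through.** **The plan's own figure.** The only powered sample size is for the primary endpoint. With event rates of 16.6% and 14.6%, a margin of 6.0%, one-sided alpha 0.025 and 90% power, the number per arm is

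(0.166 × 0.834 + 0.146 × 0.854) × (1.960 + 1.282)² / (0.06 + 0.02)² = 432.0 (unrounded normal quantiles),

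or 864 in total, as section 11.1 states. No SD, correlation or sample size is given for the four continuous measures.

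**Inputs.**
- Two-sided alpha 0.05 (section 11.6) and 1:1 allocation.
- Number analysed per arm, an assumption: 432 (half of 864), 500 (section 11.1: "an actual sample size of 1000 has been chosen") or 591 (section 4.0: "Up to 1182 qualified patients will be randomized").
- Baseline to follow-up correlation r, an assumption: 0.3 to 0.6. SD = 1 at both times.

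**Formulas.**
- SE of the unadjusted difference in visit values = √(2/n).
- Variance of ANCOVA relative to the visit-value t-test = 1 − r².
- Variance of a change-score t-test relative to the visit-value t-test = 2(1 − r), so ANCOVA relative to change = (1 − r²) / [2(1 − r)] = (1 + r)/2.
- Difference detectable with 80% power = (1.960 + 0.842) × √(2/n) × √(variance factor).

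**Effect of r, at any n.**

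| r | ANCOVA ÷ visit value, variance | Reduction in SE | ANCOVA ÷ change, variance |
|---|---|---|---|
| 0.3 | 0.91 | 4.6% | 0.65 |
| 0.4 | 0.84 | 8.3% | 0.70 |
| 0.5 | 0.75 | 13.4% | 0.75 |
| 0.6 | 0.64 | 20.0% | 0.80 |

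**Detectable difference in SD units, 80% power.**

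| n per arm | SE | Unadjusted | r = 0.3 | r = 0.4 | r = 0.5 | r = 0.6 |
|---|---|---|---|---|---|---|
| 432 | 0.0680 | 0.191 | 0.182 | 0.175 | 0.165 | 0.153 |
| 500 | 0.0632 | 0.177 | 0.169 | 0.162 | 0.153 | 0.142 |
| 591 | 0.0582 | 0.163 | 0.155 | 0.149 | 0.141 | 0.130 |

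At 500 per arm, the gain equals raising an unadjusted comparison to 500/(1 − r²) = 549, 595, 667 or 781 per arm.

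**Missing baselines.** Section 11.8.5 imputes nothing unless specified, so a complete-case ANCOVA would drop patients without a baseline. It loses its net advantage once the missing share exceeds about r² (9% at r = 0.3, 25% at r = 0.5). In a simulation of 6000 trials with 500 per arm and no true effect, the variance ratio of ANCOVA to the visit-value comparison was 0.914 at r = 0.3 and 0.630 at r = 0.6. With 5% of baselines missing at random (assumed) and replaced by the overall mean of both arms, it was 0.918 and 0.648. The mean estimate stayed within 0.001 SD of zero throughout. The simulation confirms the algebra; it is not evidence about r in this trial.

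**The case against.** The strongest reply is that nothing the trial must decide depends on this. These are additional endpoints outside the labeling sequence. The only power claim is for the primary endpoint, and the KCCQ labeling endpoint is a binary composite tested by Fisher's exact test. The t-test is valid. All of that stands, and it limits how much the point matters. It does not justify intervals wider than they need be for endpoints that are still tested at 0.05 and reported.

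The size of the gain rests on assumption. One range of r is applied to four instruments and two visits, and at r = 0.3 the gain is small. That also stands, so the figures are illustrative.

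If change from baseline is what will be tested, baseline is already in use, and the figures against the visit value do not apply. The gain is then 35% of the variance at r = 0.3, falling to 20% at r = 0.6. ANCOVA is more precise on either reading.

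A separate SAP, to which section 11.8.5 refers, might already specify adjustment. It is not among the documents supplied, so the conclusion is limited to the text at hand.

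Finally, the fix touches the no-imputation rule. It does so only for a baseline covariate, never an outcome, and purely to keep patients who have follow-up.

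**Conclusion.** The concern holds. The supplied text compares these four continuous measures without baseline adjustment, although baseline is collected before randomisation and nothing in the text rules adjustment out. With r between 0.3 and 0.6 and equal SDs (both assumed), the visit-value t-test gives up 9–36% in variance, or 5–20% in standard error. The gain from adjusting is small at the low end and material at the high end. Primary and labeling conclusions do not change, and adjustment would not remove selection into the As Treated population.

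**What to change.** - **Sections 11.8.2 and 11.8.9:** make the main comparison for the KCCQ, SF-36 and EQ-5D-5L scores and six-minute walk distance an ANCOVA of the 30-day and 1-year value on arm and the baseline value of the same measure. Report the adjusted mean difference with its 95% CI. State explicitly that the six-minute walk analysis uses the visit value. Keep the unadjusted t-test of the visit value, and the Wilcoxon test where non-normality is severe, as supportive.
- **Section 11.8.5:** allow a missing baseline covariate, and only that, to be replaced by the overall mean of both arms combined.
- **Elsewhere:** align any separate SAP text and the quality-of-life core lab reports.

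The cost is two or three sentences and a standard SAS procedure, with no new data, visits or patients.
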